#### 6.1.1. Demographics and Baseline Characteristics

The following demographics will be summarized for the FAS and the EXT-Evaluable Populations: age, age group ( $18 \leq \text{to} \leq 30$ ,  $31 \leq \text{to} \leq 40$ ,  $41 \leq \text{to} \leq 50$ ,  $51 \leq \text{to} \leq 60$ ,  $\geq 61$  years), sex, race, ethnicity, weight, height, body mass index, body mass index category ( $< 25 \text{ kg/m}^2$ ,  $\geq 25$  to  $< 30 \text{ kg/m}^2$ ,  $\geq 30$  to  $< 40 \text{ kg/m}^2$ ,  $\geq 40$  to  $< 50 \text{ kg/m}^2$ , and  $\geq 50 \text{ kg/m}^2$ ), and tobacco use (never used, current user, or former user).

#### 6.1.2. Baseline Disease Characteristics and Disease History

The following baseline disease characteristics and disease history will be summarized for all participants in the FAS Population, including, but not limited to the following:

- Disease duration (years)
- CSU family history
- Prior therapy for CSU (yes/no)
- Baseline anti-IgE biologic use (yes/no)
- Baseline IgE
- Baseline high-sensitivity C-reactive protein

- Baseline UAS7
- Baseline UAS7 categories (16-27, moderate; 28- 42, severe)
- Baseline HSS7
- Baseline ISS7
- [REDACTED]

Note: Disease duration (years) will be calculated as follows:

$$\text{Disease duration (years)} = (\text{date of randomization} - \text{date of initial CSU diagnosis} + 1) / 365.25.$$

### 6.1.3. Medical History

For participants in the FAS Population, medical history will be summarized by treatment group. This summation will include the number and percentage of participants with medical history for each body system/system organ class as documented in the eCRF.

### 6.1.4. CSU Medical History

For participants in the FAS Population, CSU medical history will be summarized by treatment group.

## 6.2. Disposition of Participant

The number of participants enrolled by country and/or site will be provided by treatment group and overall.

The following categories will be summarized by treatment group and overall for the FAS Population in the PC period:

- Number (%) of participants who were randomized
- Number (%) of participants who were treated during the PC period
- Number (%) of participants who completed treatment during the PC period
- Number (%) of participants who discontinued treatment with a primary reason for discontinuation of study drug during the PC period
- Number (%) of participants who withdrew from the study with a primary reason for withdrawal from the study during the PC period

The following categories will be summarized by treatment group and overall for the EXT-Evaluable Population during the EXT period:

- Number (%) of participants who were treated during the EXT period
- Number (%) of participants who completed treatment during the EXT period

- Number (%) of participants who discontinued study treatment with a primary reason for discontinuation of study drug during the EXT period
- Number (%) of participants who withdrew from the study with a primary reason for withdrawal from the study during the EXT period

### 6.3. Protocol Deviations

Protocol deviations recorded will be summarized and listed for the FAS during the PC period and EXT-Evaluable Population during the EXT period.

### 6.4. Exposure

For participants in the Safety Population during the PC period and the EXT-Evaluable Population during the EXT period, as well as for participants who only received povorcitinib 15, 45, or 75 mg during the overall period, exposure to the study drug will be descriptively summarized by treatment group as follows:

- **Duration of treatment with study drug (days):** Date of last dose of study drug during the specific period – date of first dose of study drug during the specific period + 1.

The average daily dose of povorcitinib and total actual dose of povorcitinib administered will be summarized by treatment group as follows:

- **Average daily dose of povorcitinib (mg/day):** Total actual povorcitinib dose taken during the specific period (mg) / (duration of treatment with povorcitinib during the specific period [days] – number of interrupted days with povorcitinib during the specific period).
- **Total actual dose of povorcitinib administered (mg):** (Total number of tablets dispensed during the specific period – total number of tablets returned during the specific period) × 15 (mg/tablet) ×  $p_T$ ,

where  $p_T$  denotes the proportion of povorcitinib among the 5 tablets taken daily (ie,  $p_T = 0$  [0/5] for the placebo group, 1/5 for the povorcitinib 15 mg group, 3/5 for the povorcitinib 45 mg group, and 5/5 for the povorcitinib 75 mg group).

The total number of tablets dispensed and returned in each period is based on information entered on the Drug Accountability eCRF. Should the dispensed drug not be returned, the actual dose taken, starting from the dispense date of the unreturned drug, will be imputed by the dose taken per the Compliance eCRF.

### 6.5. Study Drug Compliance

For participants in the Safety and EXT-Evaluable Populations, overall compliance (%) with study drug will be calculated as follows:

Compliance (%) =  $100 \times (\text{total dose actually taken during the specific period}) / (\text{total prescribed dose during the specific period})$ .

The total prescribed dose during the specific period is defined as the sum of the doses prescribed by the investigator accounting for dose interruptions during the specific period; this will be calculated as follows:

(Duration of treatment with study drug during the specific period – number of days with dose interruptions during the specific period) × 5 (tablets/day).

The total actual dose taken in a specific period will be calculated as follows:

Total number of tablets dispensed during the specific period – total number of tablets returned during the specific period.

For more details on the total number of tablets dispensed and returned, see Section 6.4.

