Contact IRT	X	X	X	X	X	X	X	X	X	X	X			Section 8.1.3
Dispense eDiary (handheld device) and instruct participant on use	X													Section 8.2.1.3
Randomization		X												Section 6.4
Dispense study drug		X	X	X	X	X	X	X	X	X				Section 6.1
Administer study drug at site		X	X	X	X	X	X	X	X	X	X			
Administer background therapy at site		X	X	X	X	X	X	X	X	X	X			
Distribute reminder card	X	X	X	X	X	X	X	X	X	X	X			Section 8.1.4
Distribute participation card	X													Section 8.1.5

Table 3: Schedule of Activities (Continued)

Visit Day (Range)	Screening	PC Period (12 Weeks)				EXT Period (24 Weeks)						Post-Treatment Follow-Up	Notes and Protocol Section
	Days -28 to -1	Baseline Day 1	Week 4 (± 3 d)	Week 8 (± 3 d)	Week 12/ EOT1 (or ET1) (± 3 d)	Week 16 (± 3 d)	Week 20 (± 3 d)	Week 24 (± 3 d)	Week 28 (± 3 d)	Week 32 (± 3 d)	Week 36/ EOT2 (or ET2) (± 3 d)	Week 44/ EOS (± 7 d)	
Administrative procedures (continued)													
Collect study drug and review drug compliance			X	X	X	X	X	X	X	X	X		Section 6.5
Follow-up phone call for eDiary compliance	X*		X†		X*								Section 8.2.1.2.1 * 1 week before visit. † 2 weeks before visit.
Review eDiary compliance		X	X	X	X	X	X	X	X	X	X		Section 8.2.1.2.2
Safety assessments													
AE assessments	X	X	X	X	X	X	X	X	X	X	X	X	Section 8.3.1
Contraception check	X	X	X	X	X	X	X	X	X	X	X	X	Section 5.3.1
Comprehensive physical examination	X				X						X		Section 8.3.2
Targeted physical examination		X	X	X		X	X	X	X	X		X	
Weight/height	X	X			X			X			X	X	Section 8.3.2 Height at screening only.
Vital signs	X	X	X	X	X	X	X	X	X	X	X	X	Section 8.3.3
12-lead ECG	X				X						X		Section 8.3.4

Table 3: Schedule of Activities (Continued)

Visit Day (Range)	Screening	PC Period (12 Weeks)				EXT Period (24 Weeks)						Post-Treatment Follow-Up	Notes and Protocol Section
	Days -28 to -1	Baseline Day 1	Week 4 (± 3 d)	Week 8 (± 3 d)	Week 12/ EOT1 (or ET1) (± 3 d)	Week 16 (± 3 d)	Week 20 (± 3 d)	Week 24 (± 3 d)	Week 28 (± 3 d)	Week 32 (± 3 d)	Week 36/ EOT2 (or ET2) (± 3 d)	Week 44/ EOS (± 7 d)	
Efficacy assessments													
PROs													
eDiary (UAS/AAS)	Daily from screening through Week 44 (or ET, if applicable)											Sections 8.2.1.3, 8.2.1.4, and 8.2.1.5 Handheld device.	
Quality of life assessments													
Laboratory assessments													
Serum FSH (WONCBP only)	X												Section 8.3.5

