6.5.1. Compliance With Povorcitinib/Placebo

Compliance with study drug will be calculated by the sponsor based on the drug accountability (eg, tablet counts) documented by the site staff and monitored by the sponsor/designee. Participants will be instructed to bring all unused study drugs with them to the study visits in order for site personnel to conduct tablet counts to assess study drug accountability.

Compliance with study drug will be calculated for the PC and EXT periods based on the following:

Within the PC period:

- The first dose will occur on Day 1 (baseline).
- The last dose will occur on the day of the Week 12 visit or the day of the last study drug administration known to the investigator (or designee) as reported in the EDC for participants who prematurely discontinue study treatment or are lost to follow-up.

Within the EXT period:

- The first dose will occur the day after the Week 12 visit.
- The last dose will occur on the day of the Week 36 visit or the day of the last study drug administration known to the investigator (or designee) as reported in the EDC for participants who prematurely discontinue study treatment or are lost to follow-up.

Participants' compliance must be within 80% to 120% assessed at each study visit by the investigator (or designee). If outside of this range, it will be considered a Protocol deviation. Participants consistently noncompliant with the study drug may be withdrawn from the study. The decision on withdrawal will be made by the investigator after consultation with the sponsor, and relevant correspondence will be archived in the site study file.

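### Tablets are counted in the period of dispensing and return, so the Week 12 pack inflates placebo-controlled compliance and dose and deflates extension values unless it is mapped to the extension

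*SAP*

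**What the plan says.** **Numerator.** SAP 6.5 defines the amount taken in a period as "Total number of tablets dispensed during the specific period – total number of tablets returned during the specific period". SAP 6.4 multiplies the same count by 15 mg and by p_T, the proportion of active tablets (0 for placebo; 1/5, 3/5 and 5/5 for the 15, 45 and 75 mg groups). On the source, SAP 6.4 says "The total number of tablets dispensed and returned in each period is based on information entered on the Drug Accountability eCRF".

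**Denominator.** SAP 6.5 uses treated days in the period, less interruptions, at five tablets a day: "Duration of treatment with study drug during the specific period – number of days with dose interruptions during the specific period) × 5 (tablets/day". SAP 6.4 divides total dose by the same net days to get average daily dose.

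**Period boundary.** Protocol 6.5.1 says of the PC period: "The last dose will occur on the day of the Week 12 visit". Of the EXT period it says: "The first dose will occur the day after the Week 12 visit".

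**Visit schedule.** In Protocol Table 3 the Week 12/EOT1 column sits under the PC period, and Protocol 8.7 says completing that visit completes the PC period. The row "Dispense study drug" is marked at Day 1 and Weeks 4, 8 and 12, then at Weeks 16 to 32. Collection is marked at Weeks 4, 8 and 12, then at Weeks 16 to 36.

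**Unreturned drug.** SAP 6.4 has one exception: "Should the dispensed drug not be returned, the actual dose taken, starting from the dispense date of the unreturned drug, will be imputed" from the Compliance eCRF.

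**The concern.** Read with the visit schedule, the counting rule gives the PC period four dispensings against three collections, and the EXT period five dispensings against six collections. The unmatched item is the Week 12 pack. It enters the PC count with no return against it. It is missing from the EXT count, although its leftovers are subtracted there. The denominators follow dosing days and are correct for each period, so numerator and denominator describe different drug.

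At stake are the planned by-period exposure and compliance summaries (SAP Appendix A, Tables 3.1.1.x and 3.1.2.x). PC dose and compliance could exceed what was prescribed, and tablet-derived EXT dose could be understated in the longer of the two treatment periods. Because the error is additive, it can also make poor PC adherence look acceptable.

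**Working it through.** The documents give no compliance figure to reproduce, so this is direct tablet accounting.

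**Inputs**
- 5 tablets/day (Protocol Table 7; SAP 6.5).
- PC 12 weeks = 84 days; EXT 24 weeks = 168 days (Protocol Table 2).
- Dispensings: 4 in PC, 5 in EXT. Collections: 3 in PC, 6 in EXT (Protocol Table 3).
- Pack size P days: **not stated**. 28 days is assumed from the four-week visit spacing, and 35 days is the upper case.
- Full adherence, no interruptions, both periods completed, all packs returned at the next visit.

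**Formulas when dispensing is mapped by visit or date**
- PC count = 4 × 5P − (3 × 5P − 420) = 420 + 5P. Compliance = (420 + 5P)/420.
- EXT count = 5 × 5P − (6 × 5P − 840) = 840 − 5P. Compliance = (840 − 5P)/840.
- Average daily dose in the 75 mg arm = 75 mg × the same ratio, because p_T = 1.

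**Results**

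| Pack | PC count / prescribed | PC compliance | EXT count / prescribed | EXT compliance | 75 mg arm, PC | 75 mg arm, EXT |
|---|---|---|---|---|---|---|
| 28 days | 560/420 | 133.3% | 700/840 | 83.3% | 100 mg/day | 62.5 mg/day |
| 35 days | 595/420 | 141.7% | 665/840 | 79.2% | 106.2 mg/day | 59.4 mg/day |

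If Day 1 and a Day 85 Week 12 visit are both counted, PC has 85 days and the 35-day case becomes 600/425 = 141.2%. Three exact 28-day packs cover only 84 days, so that case is worked on 84.

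**Incomplete adherence.** With a 28-day pack the shift is +140/420 = +33.3 points in PC and −140/840 = −16.7 points in EXT, whatever the adherence. A participant who truly took 80% would show (336 + 140)/420 = 113.3% in PC and (672 − 140)/840 = 63.3% in EXT.

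**Early EXT stoppers, 28-day pack**
- Stop on EXT day 28: (140 − 140)/140 = 0%.
- Stop on EXT day 14: nothing dispensed in EXT and 70 tablets returned, so the count is −70 against 70 prescribed, or −100%. In the 75 mg arm the dose is −70 × 15 = −1,050 mg.

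**Placebo crossovers, 28-day pack.** The Week 12 pack is their first povorcitinib. In PC it is multiplied by p_T = 0, and in EXT it is absent. For a crossover to 75 mg the missing dose is 140 × 15 = 2,100 mg of 840 × 15 = 12,600 mg, one sixth. The overall-period exposure summary in SAP 6.4 does not recover it, because it covers only participants who received povorcitinib throughout.

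**Group means.** Only participants given the Week 12 pack are affected. If 90% enter EXT and the rest score 100%, mean PC compliance is 1 + 0.9 × 140/420 = 130%.

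**With the pack assigned to the period of use:** PC 420/420 = 100%, EXT 840/840 = 100%, and 75 mg/day in both periods for the 75 mg arm.

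**The case against.** **The mapping is not stated.** The counts come from an accountability form that we cannot see. That form, or the program, may already place the Week 12 dispensing in EXT. The quantity SAP 6.5 sets out to measure is dose taken in the period, and Protocol 6.5.1 defines the periods by dosing days, so a careful programmer might do this unprompted. This stands: the error is conditional. It does not dispose of the point, because the formula counts dispensing and return rather than use. The SAP's other date rules (4.2.2 for concomitant medication, 9.2.1 for adverse events) also keep events before the first EXT dose in PC, so mapping by date would put the pack there.

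**The unreturned-drug rule might repair it.** If unreturned means not returned within the same period, the Week 12 pack would trigger imputation in PC and most or all of the PC excess would go. This makes the PC half the less secure one. On the ordinary reading the pack is returned, at Week 16, and the rule does not apply. On either reading EXT still lacks the pack.

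**The consequences are narrow.** This stands. A reader might infer that adherent participants would be recorded as protocol deviators for exceeding 120%. The documents do not support that, because Protocol 6.5.1 has the investigator assess the 80% to 120% range at each visit, not through this per-period summary. Nor do they support any effect on efficacy: no analysis population, estimand or endpoint uses tablet compliance.

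**Conclusion.** The counting rule is wrong as written and should be corrected. If the Week 12 dispensing is mapped by visit or date, a fully adherent completer of both periods scores about 133% in PC and 83% in EXT with a 28-day pack, and about 141% and 79% with 35 days. The direction does not depend on pack size, and overage makes both errors larger. Participants who stop early in EXT can have zero or negative counts. The sizes rest on an assumed pack size, equal packs and full adherence; PC group means are diluted by those who never reach EXT.

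A reader might infer that every by-period quantity is wrong for everyone who continues. That goes too far. PC povorcitinib dose in the placebo arm is zero either way. Treatment duration is date-based and correct. Combined PC plus EXT totals are unbiased for participants on povorcitinib throughout. What is exposed is by-period compliance, tablet-derived dose and average daily dose, and the crossovers' povorcitinib dose. These are descriptive outputs, which limits the weight of the point, but the correction costs almost nothing.

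**What to change.** State in SAP 6.4 and 6.5 that each dispensed pack and its return are attributed to the period in which the pack is to be taken, whatever the date of dispensing or return:

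- PC: packs dispensed at Day 1, Week 4 and Week 8, with their returns.
- EXT: packs dispensed at Weeks 12 to 32, with their returns.
- p_T follows the treatment in the pack, so a crossover's Week 12 pack carries the proportion of the assigned povorcitinib dose.

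Check how the Drug Accountability eCRF labels the Week 12 dispensing. If it already assigns it to EXT, the sentence only records what is done. The cost is one sentence in the two sections and a mapping by dispensing visit in the exposure program. No new data are needed.

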## 6.6. Prior and Concomitant Medication

Prior medications and concomitant medications will be coded using the WHO Drug Dictionary. For the FAS Population during the PC period, both prior and concomitant medications will be summarized by treatment group and overall. For the EXT-Evaluable Population during the EXT period, only concomitant medications will be summarized by treatment group and overall. For participants who received only povorcitinib 15, 45, or 75 mg during the overall period, concomitant medications will be summarized by treatment group and overall. The number and percentage of participants in all populations will be summarized by WHO drug class and WHO drug PT.

## 7. EFFICACY

[Appendix A](#) provides a list of data displays. Sample data displays are included in a separate document.

### 7.1. General Considerations

[figure not shown]
[figure not shown]
All by-visit analyses for the EXT-Evaluable Population will include the follow-up period if the data are available or unless otherwise specified. Likewise, unless otherwise stated, the strata identified in the randomization process will be used in all efficacy analyses.

### 7.2. Efficacy Parameters

[figure not shown]
#### 7.2.1. Patient-Reported Outcomes

Patient-reported outcomes and quality of life will be assessed using the following tools:

- UAS (see Section 7.2.1.1)
- AAS (see Section 7.2.1.2)
- UCT (see Section 7.2.1.3)

- 
- 
- 

- 
- 
- 
- 

#### 7.2.1.1. Urticaria Activity Score

The UAS is a composite, eDiary-recorded score with numeric severity intensity ratings (0 = none to 3 = intense/severe) for 1) the number of hives (ie, HSS) and 2) the intensity of the pruritus (ie, ISS) over the past 24 hours.

The ISS7 is defined as the 7-day sum of the daily ISS scores, and the HSS7 is also defined as the 7-day sum of the daily HSS scores.

The UAS7 is the 7-day sum of the daily UAS. The UAS7 (range: 0-42) is equal to the ISS7 (range: 0-21) plus the HSS7 (range: 0-21; see the scoring guide for further details).

The baseline UAS7 scores will be determined by summing the 7 daily UAS scores before Day 1 (ie, Day -7 to Day -1), divided by the number of nonmissing days, multiplied by 7.

Should more than 2 of the 7 days of the daily UAS scores be missing prior to Day 1, then the baseline UAS7 will be set to missing.

Similarly, the by-visit UAS7 score for postbaseline visits will be determined by summing the 7 daily UAS scores before the visit day. If more than 2 daily UAS scores out of the 7 days before the visit day are missing, the UAS7 at the visit will be set to missing.

For time-to-event endpoints, the UAS7 part will be derived similarly as above, using each nonmissing day as an anchor for any study day after Day 7. Subsequent variables, including achievement of  $UAS7 \leq 6$ ,  $UAS7 \geq 9.5$ -point improvement from baseline, HSS7 MID ( $\geq 5$ -point) improvement from baseline, and ISS7 MID ( $\geq 5$ -point) improvement from baseline, will be calculated for each nonmissing day.

[figure not shown]
The first day achieving any of the above endpoints is defined as the earliest date of achieving the event. Then, the time to event will be calculated as (date of event – Day 1 date + 1).

Participants who did not achieve the event during the PC period/EXT period will be censored as follows:

[figure not shown]
[figure not shown]
- Participants who completed the PC period through Week 12 or the EXT period through Week 36 without having the event will be censored and the censored time will be calculated as (date of last available UAS7 measurement – Day 1 date + 1).

[figure not shown]
#### 7.2.1.2. Angioedema Activity Score

[figure not shown]
The AAS eDiary records if participants have experienced a swelling episode during the previous 24 hours. If the participant responds yes, further questions are asked covering time of event, physical discomfort, impact on daily activities, appearance, and overall severity.

[figure not shown]

**7.2.1.3. Urticaria Control Test**

### 7.3. Analysis of the Primary Efficacy Parameter

The primary efficacy endpoint is the change from baseline in the UAS7, defined as the 7-day sum of the individual, daily recorded scores for HSS and ISS, at Week 12. The primary estimand and corresponding intercurrent strategies are provided in Table 4 and Table 5.

**Table 4: Estimand for Primary Endpoint**

Primary Endpoint	Population	Treatment	Population-Level Summary
Change from baseline in the weekly UAS7 at Week 12	Participants aged 18 to 65 years who have had a diagnosis of CSU for $\geq 3$ months that is inadequately controlled by second-generation H1 antihistamines	Each of the povorcitinib dose groups compared with placebo	The estimated mean change from baseline in UAS7 for each treatment group, as well as the difference in the estimated mean change from baseline in UAS7 score in each active treatment group as compared with the placebo group, at Week 12

**Table 5: Intercurrent Events and Strategies for the Primary Estimand**

Intercurrent Event	Strategies for Addressing the Intercurrent Event
Treatment discontinuation due to any reason	The data collected for the variable are used regardless of whether the participant discontinues treatment due to any reason (treatment policy strategy)
Initiation of Protocol-allowed rescue medication	The data collected for the variable are used regardless of whether the participant starts the use of any Protocol-allowed rescue medication (treatment policy strategy)

The primary analysis will be performed in the FAS. The mean change from baseline at Week 12 in weekly UAS7 score will be assessed using an MMRM to include all available data at postbaseline visits during the PC period up to Week 12. Participants who have a baseline value and at least 1 postbaseline value during the PC period will be included in the analysis. The MMRM will include change from baseline up to Week 12 as a response variable and the fixed effect of treatment group, randomization stratification factor (previous use of an anti-IgE biologic [yes or no]), visit, treatment-by-visit interaction, and covariates of baseline value and

baseline value by visit interaction. Unstructured covariance matrix will be assumed for the within-participant errors.

Compound symmetry covariance matrix will be used if the model with unstructured variance covariance does not converge. The Kenward-Roger method will be used to estimate the degrees of freedom. Missing data will not be imputed. The least squares mean estimates for each treatment group and the associated covariance matrix obtained from the MMRM will be provided and further used in the generalized MCP-mod framework.

At the MCP stage, contrast test statistics and multiplicity adjusted p-value for the contrast test will be provided for each prespecified candidate model. A dose-response relationship will be declared if at least 1 model among the set of 6 prespecified candidate models is identified to be statistically significant at the level  $\alpha = 0.025$  1-sided trend test. Once a significant dose-response is established, the best model will be selected using Akaike Information Criterion.

At the mod stage, the selected model will be used to obtain the dose-response curve and the 95% CI. The estimated dose-response curve will be presented graphically.

